The change of BMD between baseline and 6 months will also be summarized and the percent change in BMD over time will be plotted for all patients and by treatment group, respectively. A linear mixed-effect model will be fit for the data set to investigate if there is a treatment effect at different time points and if the pattern of BMD change over time differs between two groups. Similar analysis will also be performed for graft rate, serum C-telopeptide (CTX) measured over time, as well as for cytokines associated with bone loss. The incidence rate of fracture will be estimated for each arm and will be compared between the two arms using Fisher's exact test.

The change of BMD between baseline and 12 months will also be summarized for patients with and without additional steroid treatment for GVHD after allogeneic bone marrow transplant separately. Wilcoxon rank sum test will be used to assess the difference in BMD change between patients with and without prolonged steroid and other immunosuppressant use for the treatment of GVHD, either in all patients or by treatment group. A multiple linear model will be fit for the BMD at 12 months, adjusting for baseline BMD and using steroid doses in GVHD, treatment as well as steroid use in GVHD and treatment interaction as predictors.

We will summarize the change of BMD between baseline and 12 months by disease type (i.e., hematological malignancies vs. hematological disorders). Wilcoxon rank sum test will be used to assess the difference in BMD change between patients with hematological malignancies and those with hematological disorders. A multiple linear model will be fit for the BMD at 12 months, using baseline BMD, disease type, treatment arm, as well as the interaction between disease type and treatment as covariates. The fitted model will help us address the question whether or not the treatment effect is similar in these two disease types.

Based on already published data (9) on risk of skeletal-related events (SRE) with ibandronate, modeling will be conducted to determine cost-effectiveness ratio of cost per SRE avoided, with sensitivity analysis. Costs will include the potential cost of treating for SREs and the potential cost of treating adverse events due to i.v. Ibandronate. One-way sensitivity analysis varying the key assumption (SRE relative risk reduction rate from 0% to 50% in 5% intervals) over the base case will be conducted to determine if it might impact the cost-effectiveness ratio.

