Incremental Cost Effectiveness Ratio (ICER):

1.
$$\frac{(\text{Cost}_{\text{treatment}} - \text{Cost}_{\text{control}})}{(\# \text{SREs}_{\text{treatment}} - \# \text{SREs}_{\text{control}})}$$
2.
$$\frac{(\text{Cost}_{\text{treatment}} - \text{Cost}_{\text{control}})}{(\text{Months free of SREs}_{\text{treatment}} - \text{Months free of SREs}_{\text{control}})}$$

TreeAge Pro 2007 by TreeAge Software Inc., will be utilized for the cost-effectiveness calculations. The analysis will compute per-patient costs and benefits for the 12 month study period, following an intent-to-treat approach, and produce a cost-effectiveness ratio. The primary outcomes are incremental cost per percent of reduction in BMD and incremental cost per patient within one or two SD of normal BMD.

Two Incremental Cost Effectiveness Ratios (ICER) will be calculated:

1.
$$\frac{(\text{Cost}_{\text{treatment}} - \text{Cost}_{\text{control}})}{(\% \text{BMD reduction}_{\text{treatment}} - \% \text{BMD reduction}_{\text{control}})}$$
2.
$$\frac{(\text{Cost}_{\text{treatment}} - \text{Cost}_{\text{control}})}{(\# \text{Patients with normal BMD}_{\text{treatment}} - \# \text{Patients with normal BMD}_{\text{control}})}$$

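### Two of the four cost-effectiveness ratios subtract a harmful outcome as treatment minus control, so a costlier, effective drug gets a negative ratio on those two and a positive one on the others.

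*Combined protocol and SAP*

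**What the plan says.** Cost-effectiveness is secondary objective 3 in Section 1.0, covering measured BMD and modelled SREs. Section 5.0 says that the SRE modelling will yield a "cost-effectiveness ratio of cost per SRE avoided, with sensitivity analysis".

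Under the heading on incremental cost-effectiveness ratios, Section 5.0 then prints four ratios in two pairs. All four have the same numerator, "Cost}_{\text{treatment}} - \text{Cost}_{\text{control". The denominators, given here as formula source, are:

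- SRE pair, first ratio: "SREs}_{\text{treatment}} - \# \text{SREs}_{\text{control"
- SRE pair, second ratio: "Months free of SREs}_{\text{treatment}} - \text{Months free of SREs}_{\text{control"
- BMD pair, first ratio: "BMD reduction}_{\text{treatment}} - \% \text{BMD reduction}_{\text{control"
- BMD pair, second ratio: "Patients with normal BMD}_{\text{treatment}} - \# \text{Patients with normal BMD}_{\text{control"

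Between the two pairs the plan gives the unit of analysis: "The analysis will compute per-patient costs and benefits for the 12 month study period". The key assumption to be varied in the one-way sensitivity analysis is the "SRE relative risk reduction rate from 0% to 50% in 5% intervals". The primary endpoint paragraph of Section 5.0 assumes a mean BMD reduction of 12% on control and 0.1% on ibandronate.

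**The concern.** Events avoided by a treatment are events on control minus events on treatment. The printed SRE denominator is the reverse, so the formula contradicts the quantity that the plan says it will estimate. The ratio on percent BMD reduction has the same form: a reduction is a loss, and the denominator is loss on treatment minus loss on control.

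The sign of an incremental ratio carries meaning. When the denominator measures benefit, a positive ratio with added cost is the ordinary trade-off of paying more for a better outcome, and a negative ratio signals that one option dominates. In each printed pair, one denominator is a harm and the other a benefit, yet both are taken as treatment minus control. The same trial result would therefore give opposite signs within each pair, and no single reading rule fits all four ratios.

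**Working it through.** The plan states no numerical cost-effectiveness ratio, so there is no figure to reproduce. The check is on the sign of each printed formula.

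**Inputs from Section 5.0:** mean BMD reduction of 12% (control) and 0.1% (treatment); SRE relative risk reduction (RRR) from 0% to 50%; the four formulas as printed.

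**Assumptions not in the documents, for illustration only:** added cost of ibandronate of +1,000 to +5,000 currency units per patient; control SRE rate of 0.05 to 0.20 per patient.

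**Step 1: signs for a costlier, effective drug.**

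| Denominator (treatment − control) | Outcome is | Denominator | Printed ratio |
|---|---|---|---|
| SREs | harm | negative | negative |
| Months free of SREs | benefit | positive | positive |
| Percent BMD reduction | harm | negative | negative |
| Patients with normal BMD | benefit | positive | positive |

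**Step 2: BMD ratio with the plan's own means.** The denominator is 0.1 − 12 = −11.9 points. For an added cost X, the printed ratio is −X/11.9:

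- X = 1,000: −1,000/11.9 = −84
- X = 5,000: −5,000/11.9 = −420

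Written as control minus treatment, the denominator is 12 − 0.1 = +11.9. The ratios become +84 and +420 per percentage point of loss avoided.

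**Step 3: SRE ratio.** With control rate r, the treatment rate is r(1 − RRR), so the printed denominator is r(1 − RRR) − r = −r × RRR. This is negative for every RRR from 5% to 50%, and zero at 0%. With an added cost of 2,000:

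| r | RRR | Printed denominator | Printed ratio | Control − treatment |
|---|---|---|---|---|
| 0.05 | 25% | −0.0125 | −160,000 | +160,000 |
| 0.10 | 5% | −0.005 | −400,000 | +400,000 |
| 0.10 | 25% | −0.025 | −80,000 | +80,000 |
| 0.10 | 50% | −0.05 | −40,000 | +40,000 |
| 0.20 | 25% | −0.05 | −40,000 | +40,000 |

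**Step 4: all four combinations of cost and effect** (cost difference ±2,000, SRE difference ±0.025 per patient).

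| Drug is | Printed ratio | Control − treatment |
|---|---|---|
| costlier, fewer SREs | −80,000 | +80,000 |
| costlier, more SREs | +80,000 | −80,000 |
| cheaper, fewer SREs | +80,000 | −80,000 |
| cheaper, more SREs | −80,000 | +80,000 |

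Read as a cost per SRE avoided, the printed formula is positive when the drug is costlier and harmful, and negative in the ordinary trade-off case. The absolute values agree in every row.

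**Step 5: units.** With r = 0.10, RRR = 25% and 100 patients per arm, per-patient cost over per-patient SREs is 2,000/(−0.025) = −80,000. Total cost over total SREs is 200,000/(−2.5) = −80,000. Either consistent reading gives the same ratio when the arms are equal.

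**The case against.** The strongest reply is that this is a matter of labelling. The plan says in words what the SRE ratio is meant to be, the magnitudes are right, and an analyst can see the cost difference in the numerator. Reversing the denominator does not make the sign self-explanatory either: a corrected ratio is negative both for a cheaper, better drug and for a costlier, worse one, so cost and effect must be read separately in any case. All of this is true, and it limits the consequence. It does not remove the contradiction between the stated quantity and the formula, or the opposite signs within each pair.

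The BMD half can be contested further. The plan labels that outcome as cost per percent of BMD reduction, without the word avoided, so the formula matches its own label. Section 5.0 also speaks of percent change; if losses were entered as signed changes, the same formula would give −0.1 − (−12) = +11.9. But both the formula and the primary endpoint are worded as a reduction, so 12 and 0.1 are the natural entries and the denominator is −11.9. That the sign depends on an unstated coding is itself a reason to fix the wording.

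A reader might also infer, from the number signs in two denominators, that total counts are set against per-patient costs and that the ratios are distorted by arm size. The documents do not support this. The plan puts costs and benefits alike on a per-patient basis, no formula labels cost as per-patient or total, and Section 5.0 specifies equal randomization. The number sign is loose notation that should be defined.

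Nor is the 0% end of the sensitivity range an error. It is the natural no-effect bound, and an incremental ratio is undefined there whichever way the denominator is taken. What to report at that point is a presentational choice.

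**Conclusion.** The point holds as a sign error in two of the four ratios. For SREs, the printed formula contradicts the plan's stated target. For percent BMD reduction, the denominator is −11.9 points under the plan's own means when losses are entered as positive reductions. The sign reversal holds for any positive added cost and any positive benefit; the cost and SRE rates used above only illustrate its size.

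A reader might infer that a costlier drug would end up reported as cost-saving. That would require ignoring the cost difference, which is the numerator of every ratio. The supportable conclusion is narrower: the sign would mislead anyone who reads the ratio alone, and the four ratios would disagree in sign for one result. The magnitudes, the primary efficacy comparison, the sample size, the interim boundaries and the safety rule are not affected. It merits correction because the analysis is a named secondary objective and the correction is free.

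**What to change.** In Section 5.0:

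- Write the SRE denominator as SREs on control minus SREs on treatment (SREs avoided).
- Write the BMD denominator as percent reduction on control minus percent reduction on treatment. Label the outcome as incremental cost per percentage point of BMD loss avoided, and state that losses are entered as positive numbers.
- Leave the ratios for months free of SREs and patients with normal BMD in their present direction.
- As side notes, define SREs as a mean per patient and normal BMD as a proportion, to match the stated per-patient analysis. At 0% risk reduction, report the cost difference with no health gain in place of a ratio.
- Report the cost difference and the effect difference beside each ratio, since the sign alone does not separate the cases even after correction.

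The cost is a text change in the SAP. No extra data, patients or visits are needed.

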3.0 Patient Eligibility

The study eligibility requirements will include the following inclusion/exclusion criteria:

3.1 Inclusion criteria:

- 1) Age greater than or equal to 18 years.
- 2) Patients with the diagnosis of hematologic malignancies or hematological disorders, who are immediately post- allogeneic bone marrow transplantation.
- 3) Female patients of childbearing potential (i.e. no hysterectomy, no loss of menses for 12 consecutive months), must be willing to use contraception.
- 4) Negative pregnancy test in premenopausal patients.
- 5) Patients with GVHD or infections can be entered only if they respond to treatment and become controlled.
- 6) Dental considerations: patients with negative dental screening for jaw osteonecrosis 0-3 months prior to their transplant and patients that do not have a plan for tooth extraction in the near future.

3.2 Exclusion criteria:

- 1) Patients with documented relapsed malignancy or recurrence of the original hematological disorder after the transplant, uncontrolled acute GVHD, or uncontrolled infection.
- 2) Patients with hypocalcemia of less than 8.4 (corrected to account for the albumin level).
- 3) Patients with hypercalcemia >12.2 , due to a cause not related to their hematological malignancy or hematological disorder (i.e. hyperparathyroidism, multiple myeloma).
- 4) Hypersensitivity to Ibandronate or other bisphosphonates.
- 5) Pre-existing osteoporosis, defined as a bone density T-score of -2.5 S.D. or less.
- 6) Renal insufficiency (calculated creatinine clearance < 30 ml/min).
- 7) Patients already on bisphosphonates (over the past two years), calcitonin, anabolic steroids, or daily oral fluoride supplement.
- 8) Myeloma patients who have previously been on bisphosphonates over the past two years and/or have active bone lesions.
- 9) If corrected calcium is above 10.3 and the iPTH is elevated or normal, the patient will be excluded from the study.
- 10) Patients with a 25-hydroxyvitamin D concentration <20 ng/ml and evidence of osteomalacia (low ionized calcium and elevated intact PTH).
- 11) Patients with recent tooth extraction with signs of incomplete healing or infection will be excluded.

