4.0 Treatment/study Plan

Patients who had hematological malignancies or hematological disorders and underwent allogeneic bone marrow transplantation are eligible to participate in the study. Members of the research team

will enroll eligible patients who meet the inclusion criteria in the study after obtaining agreement of their transplant physician. Patients with GVHD or infections can be entered only if they respond to treatment and become controlled.

As part of standard care for pre-BMT work up, all patients will have their 25(OH) Vit D levels checked. Patient with vitamin D deficiency (< 20 ng/ml) will be supplemented to adequate level (≥ 20 ng/ml).

Patients will then be randomized into the following two groups: 1) treatment: Ibandronate 3 mg intravenously over 15-30 seconds for 4 doses at 0-1.5, 3, 6, and 9 months free of charge; or 2) control: Patients will only receive daily oral calcium and vitamin D supplements. Patient's prior vitamin D supplement status will be considered as one of the randomization factor. After entering the trial, all patients will receive 500 mg of elemental calcium carbonate and Vitamin D Analog 400 IU orally twice daily for 12 months to be taken at home during the trial. Patients who do not tolerate the calcium pills provided by the trial are allowed to take another brand of calcium/vitamin D at home as tolerated with equivalent dosing. Patients who are still on weekly Ergocalciferol have the option of holding their daily vitamin D 400 IU twice daily and must resume the daily vitamin D when they are off the weekly Ergocalciferol.

BMD at lumbar spine, femoral neck and total hip will be determined at baseline (up to 3 months prior to the transplant or prior to the enrollment), 6, 12 months (± 4 weeks) post transplants for all patients in both groups by DEXA at MDACC. The change of BMD between baseline and 12 months in both Ibandronate treatment and control groups will be summarized and analyzed for statistical significance.

The members of the research team will collect data and/or blood for the following:

1. Bone turnover marker, the serum CTX will be measured at baseline, 3, 6, and 12 months (± 4 weeks)
2. Routine laboratory monitoring includes calcium, magnesium, alkaline phosphatase, albumin, and creatinine at baseline and at 3, 6, 9, and 12 months (± 4 weeks) post-transplant.

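### The normal-BMD cost-effectiveness ratio divides by a raw count that ignores entry BMD and has no fixed cut-off, which adds avoidable noise (not bias) to its denominator

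*Combined protocol and SAP*

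**What the plan says.** All of this is in the combined protocol and SAP.

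- **The outcome.** Section 5.0 lists two measured outcomes for the cost-effectiveness analysis. The second is the "incremental cost per patient within one or two SD of normal BMD".
- **The formula.** "Two Incremental Cost Effectiveness Ratios (ICER) will be calculated", and only one of them concerns normal BMD. Its denominator is the count of "Patients with normal BMD", treatment minus control. The count is not divided by arm size, and no skeletal site, reference score or visit is given for it.
- **Time frame.** "The analysis will compute per-patient costs and benefits for the 12 month study period, following an intent-to-treat approach". A 12-month count is the natural inference, but it is not stated.
- **Entry.** Section 3.2 excludes "Pre-existing osteoporosis, defined as a bone density T-score of -2.5 S.D. or less". Patients may therefore enter on either side of one SD or two SD below normal.
- **Randomisation.** Section 4.0 says "Patient's prior vitamin D supplement status will be considered as one of the randomization factor", and its description of the two strata uses prior Ergocalciferol only. Entry BMD is not named.
- **Use of entry BMD elsewhere.** In Section 5.0, "A multiple linear model will be fit for the BMD at 12 months, adjusting for baseline BMD". The other measured ratio uses percent reduction in BMD, which is relative to baseline by definition.
- **Sensitivity analysis.** The economic plan specifies "One-way sensitivity analysis varying the key assumption (SRE relative risk reduction rate from 0% to 50% in 5% intervals". The BMD cut-off is not varied.

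**The concern.** Whether a patient has normal BMD at 12 months depends heavily on where that patient started. A raw difference in counts treats any chance difference between the arms at entry as if it were part of the outcome. With about 60 evaluable patients per arm that difference can be several patients, and it falls in the denominator of a ratio, where noise is magnified. Section 5.0 uses entry BMD in its 12-month regressions and in the companion ratio, so this ratio is the exception.

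The second strand is the definition. Two cut-offs are mentioned for one ratio, and nothing says which applies or whether both will be reported. The cost difference in the numerator is the same either way, so the reported cost per patient with normal BMD can depend on a choice that the plan has not made.

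**Working it through.** **Inputs from Section 5.0:** mean BMD loss 12% (control) and 0.1% (ibandronate); common SD 0.23; two-sided 0.05; 80% power; 60 per arm; 40% drop-out.

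**Assumptions, because the documents give no entry distribution:** entry T-score normal with SD 1 and mean 0, -0.5 or -1.0, truncated at -2.5; one T-score unit equal to 11% of BMD (12% as a variant); SD of change 0.23 as planned, or 0.08 or 0.05 as smaller alternatives.

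**1. The plan's sample size reproduces.** The difference is 0.12 - 0.001 = 0.119. Then n = 2 × (1.96 + 0.84)² × 0.23² / 0.119² gives 59 per arm after rounding up, against 60 planned. Power at 60 per arm is 0.803. Enrolment is 120 / 0.60 = 200. So 60 per arm is a fair scale for the count.

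**2. Chance imbalance at entry.** If a share p is normal at entry, the SD of the between-arm difference in counts is sqrt(2 × 60 × p × (1 - p)).
- p = 0.50: 5.5 patients, 95% range about ±11.
- p = 0.60: 5.4 patients, or sqrt(2 × 0.6 × 0.4 / 60) = 0.089, which is 8.9 points.
- p = 0.84: 4.0 patients, 95% range about ±8.

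**3. How much reaches the 12-month denominator.** In simulated trials (60 per arm), each extra patient normal at entry in one arm moved the denominator by about 0.23 to 0.45 patient at SD 0.23, and by about 0.5 to 0.86 at SD 0.05 to 0.08. Applied to the 5.4 patients above, this is 0.23 × 5.4 = 1.2 to 0.45 × 5.4 = 2.4 patients at the plan's SD, and 0.5 × 5.4 = 2.7 to 0.86 × 5.4 = 4.6 at the smaller SDs. For comparison, with a mean entry T-score of -1.0 and a one-SD cut-off, the expected denominator is 0.185 × 60 = 11 patients at SD 0.23 and 0.332 × 60 = 20 at SD 0.08.

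**4. What adjustment gains.** The adjusted estimate comes from a logistic model on arm and entry BMD, averaged over all patients. Adjusted and unadjusted differences agree on average. At the one-SD cut-off:
- SD 0.23: the SE falls from 8.9-9.0 to 8.5 points. Variance reduction is 1 - (8.5/8.9)² = 9% to 1 - (8.5/9.0)² = 11%.
- SD 0.08: the SE falls from 8.2 to 6.5 points. Variance reduction is 1 - (6.5/8.2)² = 37%.

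**5. What the cut-off does.** Expected difference in percentage points, with one T unit = 11%:

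| SD of change | Mean entry T-score | One SD | Two SD | Ratio |
|---|---|---|---|---|
| 0.23 | -1.0 | 18.4 | 18.2 | 1.0 |
| 0.23 | -0.5 | 18.8 | 17.2 | 1.1 |
| 0.08 | -0.5 | 35 | 25 | 1.4 |
| 0.05 | 0 | 36 | 15 | 2.4 |

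At SD 0.23 and mean 0 the change is about 16%. With one T unit = 12% and mean 0, the figures are 10.9 against 8.9 patients at SD 0.23 (ratio 1.2) and 19.7 against 7.3 at SD 0.05 (ratio 2.7). At mean -1 and SD 0.05 they are 20.1 against 18.0 (ratio 1.1).

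**6. Why noise in this denominator matters.** With the plan's means and SD of 0.23, and mean entry T-scores of -0.5 or -1, the denominator was zero or negative in about 3% of simulated trials. If the control loss were 6% (assumption), this rose to about 3% to 21% across settings. In those trials the ratio is undefined or changes sign.

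**The case against.** The strongest reply is that this is a randomised 1:1 comparison. A reader might infer that a patient who enters low and loses nothing counts against ibandronate, or that the ratio partly measures who was enrolled. The documents do not support that reading. Such patients are expected equally in both arms, so the expected difference reflects treatment only, and adjusted and unadjusted estimates agree on average. A control who enters high, loses bone and stays normal is a feature of any threshold outcome. This part of the reply stands in full, and the issue is precision.

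It also stands that the gain is small at the plan's own SD. There, imbalance in normal status at entry explained only 5-6% of the variance of the 12-month difference at mean entry T-scores of -0.5 and -1.0, and the cut-off hardly moved the denominator. The larger figures need a smaller SD of change and an entry distribution that the documents do not give. The ratio is one of two under a secondary objective, with no hypothesis test attached.

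On the cut-off, the wording may mean that both will be reported. That is possible, but the plan lists a single ratio for normal BMD and does not say so. A reader might also infer an intention to choose after seeing the counts. Nothing in the text shows this; the choice is simply not fixed.

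What survives is that entry BMD is measured, predicts the outcome and is used elsewhere in Section 5.0, but is left out here. The definition of normal is also incomplete.

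**Conclusion.** The point holds as a minor one about precision and definition. The denominator is a raw count difference with no link to entry BMD, and its cut-off is open. This does not bias the ratio, and chance imbalance carries over only in part. Adjustment would cut the variance by about 10% at SD 0.23 and by about 35-40% if the SD is near 0.08. The cut-off is nearly immaterial at 0.23 (at most about 16% with one T unit = 11%, about 22% with 12%). It can change the denominator 1.4- to 2.4-fold at SDs of 0.05 to 0.08 with a mean entry T-score of -0.5 or 0, and makes little difference at a mean of -1.

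These sizes rest on the assumed entry distribution, the assumed percent of BMD per T unit and 60 evaluable patients per arm. The count is taken to be at 12 months, which is inferred from the study period. The randomisation appendix is not in the text available; Section 4.0 describes its strata by Ergocalciferol status only.

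**What to change.** In Section 5.0, replace the raw count in the second measured ratio with the difference between arms in the proportion of patients with normal BMD at 12 months, standardised for entry BMD. Fit a logistic model on arm and entry BMD, predict each patient's probability under both arms, and average over all patients. A difference in proportions also matches the per-patient costs that the plan already intends to compute.

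State in advance:
- one cut-off and its reference score, for example a T-score of -1 or above;
- one skeletal site, since three are measured;
- the visit at which the count is taken;
- the two-SD cut-off as a named sensitivity analysis.

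Restricting the count to patients who were normal at entry is not a good substitute. It would discard 40% of patients if 60% start normal, and it could not credit anyone who enters low and improves.

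The cost is one extra model and slightly longer SAP wording. Section 4.0 already provides the baseline DEXA, so no new data, visits or patients are needed.
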